2.1 Objectives

The objective of this clinical investigation is to confirm the safety and efficacy of BIOTRONIK's Sentus QP leads in a clinical investigation to support regulatory approval as well as a long term post-approval evaluation of the devices in the United States. The safety objective of the clinical investigation is to assess the safety of the Sentus QP lead by the analysis of the lead related complications during 6 months after implantation. The efficacy (performance) objective of the clinical investigation is to assess if pacing thresholds of the lead are in an acceptable range at 3 months after implantation. The post-approval objective of the clinical investigation is to assess the safety of the Sentus QP lead by the analysis of the lead related complications through 5 years post-implant.

2.2 Study Endpoints and Hypotheses

The following endpoints have been defined to confirm the safety and efficacy of the investigational devices.

2.2.1 Primary Endpoint 1: Sentus QP Related Complication-Free Rate through 6 Months (Pre-Market Analysis)

The purpose of primary endpoint 1 is to evaluate the Sentus QP related complication-free rate through 6 months post-implant. The Sentus QP related complications that will be assessed in this primary endpoint are defined in Section 6.6.1. The parameter of interest $p_{Complication}^{SentusQP}$ is the complication-free rate per subject, which will be calculated by (1 - the number of subject with one or more complications divided by the number of subjects) in percent. The period of observation starts after successful implantation of the Sentus QP lead.

The following hypotheses have been defined to evaluate the primary endpoint "Sentus QP related complication-free rate through 6 months":

H₀: Complication-free rate through 6 months post-implant is $\leq 90.0\%$

H_a: Complication-free rate through 6 months post-implant is $> 90.0\%$

A rejection of the null hypothesis (H_0) would demonstrate evidence that the complication-free rate is greater than 90.0%.

2.2.2 Primary Endpoint 2: Percentage of Subjects with Acceptable Pacing Threshold in Permanently Programmed Vector at 3 Months (Pre-Market Analysis)

The purpose of primary endpoint 2 is to evaluate the LV lead pacing threshold for the permanently programmed pacing vector at 3 months post-implant. Specifically, the percentage of subjects with an acceptable LV pacing threshold in the permanently programmed vector at the 3-month visit ($p_{acceptable}^{PaThres}$) will be determined. LV threshold values of $\leq 2.5V$ at 0.4 ms in the permanently programmed vector, defined as the permanent pacing vector at the beginning of the 3-month visit interrogation, will be considered acceptable.

The following hypotheses have been defined to evaluate the primary endpoint “Percentage of subjects with acceptable pacing threshold in permanently programmed vector at 3 months”:

H_0 : Acceptable LV threshold rate at 3 months post-implant is $\leq 88.0\%$

H_a : Acceptable LV threshold rate at 3 months post-implant is $> 88.0\%$

A rejection of the null hypothesis (H_0) would demonstrate evidence that the rate of acceptable LV pacing thresholds is greater than 88.0%.

2.2.3 Primary Endpoint 3: Sentus QP Related Complication-Free Rate through 5 years (Post-Approval Analysis)

The purpose of primary endpoint 3 is to evaluate the long-term Sentus QP related complication-free rate through 5 years post-implant. The Sentus QP related complications that will be assessed in this primary endpoint are defined in Section 6.6.2. The parameter of interest $p_{Complication}^{SentusQP}$ is the complication-free rate per subject, which will be calculated by (1 - the number of subject with one or more complications divided by the number of subjects) in percent. The period of observation starts after successful implantation of the Sentus QP lead.

The following hypotheses have been defined to evaluate the primary endpoint “Sentus QP related complication-free rate through 5 years”:

H_0 : Complication-free rate through 5-years post-implant is $\leq 92.5\%$

H_a : Complication-free rate through 5-years post-implant is $> 92.5\%$

A rejection of the null hypothesis (H_0) would demonstrate evidence that the complication-free rate is greater than 92.5%.

2.2.4 Secondary Endpoints

The following secondary endpoints will be evaluated during this clinical investigation. There are no formal tests of hypothesis associated with the secondary endpoints. Secondary endpoints 1 through 6 will only be evaluated as

part of the pre-market analyses. Secondary endpoint 7 and 8 will be evaluated as part of the post-approval analyses.

2.2.4.1 Sentus QP pacing threshold in permanently programmed vector at 3 months per lead model

The purpose of the secondary endpoint is to evaluate the LV lead pacing threshold for the permanently programmed pacing vector at 3 months post-implantation in the four different lead types, Sentus OTW QP L, Sentus OTW QP S, Sentus OTW QP S/49, and Sentus OTW QP L/49. Specifically, the percentage of subjects with an acceptable LV pacing threshold in the permanently programmed vector at the 3-month visit will be determined for both leads. LV pacing threshold values of $\leq 2.5V$ at 0.4 ms in the permanently programmed vector, defined as the permanent pacing vector at the beginning of the 3-month visit interrogation, will be considered acceptable.

2.2.4.2 Sentus QP pacing threshold in novel vectors at 3 months

The purpose of this secondary endpoint is to evaluate the LV lead pacing threshold for the novel pacing vector at 3 months post-implantation. Specifically, the percentage of subjects with at least one acceptable LV pacing threshold in the novel vectors at the 3-month visit will be determined. LV pacing threshold values of $\leq 2.5V$ at 0.4 ms in the novel vectors will be considered acceptable. Novel vectors are defined as all vectors utilizing one of the two distal LV rings (LV3 or LV4).

2.2.4.3 Sentus QP R-wave sensed amplitude at 3 months per lead model

The purpose of this secondary endpoint is to evaluate the LV lead sensing amplitude at 3 months post-implantation. Specifically, the percentage of subjects with acceptable LV sensing amplitude at the 3-month visit will be determined. R-wave sensed mean amplitude of $\geq 2mV$ will be considered acceptable.

2.2.4.4 Sentus QP pacing impedance at 3 months per lead model

The purpose of this secondary endpoint is to evaluate the LV lead pacing impedance at 3 months post-implantation. Specifically, the percentage of subjects with acceptable LV pacing impedance at the 3-month visit will be determined. LV impedance values of >200 Ohms and <2000 Ohms will be considered acceptable.

2.2.4.5 Sentus QP Time to first complication

The purpose of this secondary endpoint is to evaluate the Sentus QP related complication-free rate through 6 months post-implant by the Kaplan-Meier method.

2.2.4.6 Percentage of subjects successfully reprogrammed to resolve phrenic nerve stimulation or high pacing threshold during the study period

The purpose of this secondary endpoint is to evaluate the effectiveness of electrical lead repositioning to resolve phrenic nerve stimulation or high LV pacing thresholds. Specifically, the percentage of subjects in which phrenic nerve stimulation or high LV pacing thresholds which could be resolved by vector reprogramming during the study period will be determined in relation to all subjects in which it was attempted to resolve phrenic nerve stimulation or high LV pacing thresholds by electrical repositioning.

2.2.4.7 Sentus QP Related Complication-Free Rate through 5 years per lead model

The purpose of this secondary endpoint is to evaluate the long-term Sentus QP related complication-free rate through 5 years post-implant per lead model. The Sentus QP related complications that will be assessed in this endpoint will be those defined in Section 6.6.2

2.2.4.8 Sentus QP Lead Safety – Individual 5-year adverse event rates

The purpose of this secondary endpoint is to evaluate each of the individual types of adverse events contributing to primary safety endpoint 3. The Sentus QP related complications that will be assessed in this endpoint will be those defined in Section 6.6.2.

2.2.5 Additional Data of Interest

Additional information will be collected to characterize the study population, implanted system, and progress of the clinical investigation. The collected data will include baseline demographics, comorbidities, implanted system and implantation experience, system revision, Sentus QP extractions, returned product analysis, and compliance. The data will be statistically analyzed, where appropriate. Specifically, further data of interest will include:

- Demographics, including age and gender
- Baseline New York Heart Association (NYHA) class
- Historical left ventricular ejection fraction (LVEF), if obtained within 6 months prior to enrollment
- Implanted devices, including pulse generator and other leads
- Implantation site and, if available, implant approach
- Approximate vessel diameter at Sentus QP lead tip (at final lead position, when this information is available from a routine venogram performed during implant)
- Reason for inability to place Sentus QP lead

- Adverse events related to implant procedure, pulse generator, or other implanted leads
- Sentus QP lead performance at 6 and 12 months post-implant plus at additional required follow-up visits (i.e., 18 months, 24 months), including R-wave sensing, pacing impedance, and pacing threshold
- Revisions to implanted system and reason for revision
- Results from returned product analysis
- Compliance to protocol requirements and study visit schedule
- Sentus QP pacing threshold in novel vectors (optional)

2.3 Statistical Design, Method, and Analytical Procedures

2.3.1 Pre-Market Analyses Cohort

A pre-market cohort for analysis of primary endpoints 1 and 2 and secondary endpoints 1 through 6 will be comprised at the time when 231 completed 6 month follow-ups and 282 completed 3 month follow-ups have occurred. Follow-ups will be considered complete once entered in the EDC system and case report forms are electronically signed by the investigator.

The pre-market analyses cohort is defined as the population of subjects who were implanted (or had an implant attempt) on or before the implant date of the last subject to reach the latter of the 231st completed 6 month follow-up or 282nd completed 3 month follow-up.

2.3.2 Primary Endpoint 1 Analysis

The analysis population for primary endpoint 1 will include all subjects who provided informed consent, met the enrollment criteria, and in whom a Sentus QP lead was successfully implanted. The common scenarios listed below will be taken into account for analysis of primary endpoint 1:

- Subjects who completed a 6 month follow-up or experienced an adverse event (as defined in Section 6.6.1) prior to reaching the 6 month follow-up time point will be included in the endpoint evaluation.
- Subjects without an adverse event (as defined in Section 6.6.1) who exit the study prior to the 6-month follow-up are excluded from the analysis population to avoid an overestimation of the complication-free rate.
- Subjects that were not successfully implanted due to a Sentus QP lead related complication (such as coronary sinus dissection caused by the Sentus QP lead) will be included in the population.
- Any subject with a missing 6 month follow-up, who completes a subsequent follow-up (e.g. 12 month follow-up or interim follow-up) will be included in the evaluation.

Primary endpoint 1 will be evaluated by performing an exact, binomial test comparing the observed proportion (overall complication-free rate at 6 months) to the performance goal of 90.0%. The lower, two-sided 95% confidence bound for the overall complication-free rate must be greater than 90.0%.

2.3.3 Primary Endpoint 2 Analysis

For primary endpoint 2, only subjects who provide informed consent, met the enrollment criteria, and in whom a Sentus QP lead was successfully implanted will be included. The common scenarios listed below will be taken into account for analysis of primary endpoint 2.

- Any subjects not successfully implanted due to a Sentus QP lead related adverse event will be included in the analysis for primary endpoint 2 as a failure.
- For successfully implanted subjects that missed a 3 month visit or did not undergo threshold testing of the LV lead at the 3 month visit, or completed threshold testing at a pulse width other than 0.4 ms, missing data points will be imputed according to Section 2.5.4.

Primary endpoint 2 will be evaluated by performing an exact, binomial test comparing an observed proportion (rate of acceptable LV pacing thresholds at the permanently programmed pacing vector at 3 months) to 88.0%. The lower, two-sided 95% confidence bound for the percentage of subjects with an acceptable LV pacing threshold in the permanently programmed pacing vector must be greater than 88.0%.

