1.4.1 Primary Endpoint 1 Results

The purpose of primary endpoint 1 is to evaluate the Sentus QP related complication-free rate through 6 months post-implant. Reported adverse events that were related to the implanted CRT-D system and/or implant procedure were adjudicated by the CEC. Events that occurred prior to or on the date of the 6 month follow-up and were adjudicated by the CEC as meeting the primary endpoint criteria were included in the calculation of the primary endpoint 1 complication-free rate. For the purposes of the primary endpoint 1 analysis, evaluable subjects are those who were included in the pre-market cohort and either completed a 6 month follow-up visit (n = 274), experienced an endpoint related adverse event but exited the study prior to reaching the 6 month follow-up

(n = 2), did not complete a 6 month follow-up visit but did complete a subsequent visit (n = 3), or had an unsuccessful implant due to a Sentus QP lead related complication (n = 0). Subjects in the pre-market cohort that did not have a successful Sentus QP implant were not included in the endpoint 1 analysis (unless, as noted above, the unsuccessful implant was due to a Sentus QP lead related complication). The total number of evaluable subjects for primary endpoint 1 was 279.

Analysis

Primary endpoint 1 was evaluated by performing an exact, binomial test comparing the observed proportion (complication-free rate at 6 months) to 90.0%.

Of the 279 evaluable subjects for primary endpoint 1, eight subjects had an event that met the primary endpoint criteria, were adjudicated by the CEC as related to the Sentus QP lead, and occurred prior to or on the date of the 6 month follow-up. The complication-free rate through 6 months post-implant is 97.1% (271/279), 95% CI of 94.4% to 98.8%, $p < 0.0001$.

Table 2 provides a summary of the eight primary endpoint 1 adverse events.

Table 2: Primary Endpoint 1 Adverse Event Summary

Adverse Event Type	Subjects with AE	% with AE	Number of AEs	Rate (per subject year)
Lead dislodgement	4	1.43%	4	0.028
Extracardiac stimulation	3	1.08%	3	0.021
Lead impedance out of range, high	1	0.36%	1	0.007
Total	8	2.87%	8	0.055

Total number of implanted subjects = 279; Subject years since successful implant = 144.7

Conclusion

The results indicate that the complication-free rate through 6 months post-implant is greater than 90.0%; therefore, primary endpoint 1 is met.

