1.4.2 Primary Endpoint 2 Results

The purpose of primary endpoint 2 is to evaluate the LV lead pacing threshold for the permanently programmed pacing vector at 3 months post-implant. Specifically, the percentage of subjects with an acceptable LV pacing threshold in the permanently programmed vector at the 3 month follow-up will be determined. An acceptable LV threshold was defined as being ≤ 2.5 V at a pulse width of 0.4 ms in the pacing vector programmed at the beginning of the 3 month follow-up.

For the purposes of the primary endpoint 2 analysis, evaluable subjects are those who were included in the pre-market cohort and either completed a threshold test at a pulse width of 0.4 ms at the 3 month follow-up (n = 276), did not have a threshold test at or missed the 3 month follow-up but had Home Monitoring data meeting specific consistency criteria available for imputation (n = 3), had a subsequent follow-up visit with threshold test at a pulse width of 0.4 ms (n = 7), or were not successfully implanted due to a Sentus QP lead related adverse event (n = 0). A total of 286 subjects were included in the evaluation of primary endpoint 2.

[figure not shown]
Analysis

Primary endpoint 2 was evaluated by performing an exact, binomial test comparing the observed proportion (rate of acceptable LV pacing thresholds at 3 months) to 88.0%.

Of the 286 evaluable subjects for primary endpoint 2, 267 subjects had an acceptable LV threshold for a rate of 93.4%, 95% CI of 89.8% to 96.0%, p=0.002.

Figure 7 provides a histogram showing the Sentus QP pacing threshold values in the permanently programmed vector at 3 months. The acceptable threshold maximum of 2.5 V is indicated by the vertical line. Three subjects had a result of no capture possible during the threshold test and are not displayed in Figure 7. These three subjects were considered as failures in the analysis of primary endpoint 2.

Figure 7: Sentus QP Pacing Threshold Values at the 3 Month Follow-up

Conclusion

The results indicate that the proportion of subjects with an acceptable threshold value in the permanently programmed vector at the 3 month follow-up is greater than 88.0%; therefore, primary endpoint 2 is met.

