2.4 Estimated Sample Size

2.4.1 Pre-Market Analyses

The sample size required to evaluate primary hypotheses 1 and 2 was estimated using the following design criteria:

- Study design: non-randomized
- Test basis: exact binomial test
- Type I error, alpha: 2.5% (one-sided)
- Statistical power: 80% for acceptance of both primary Alternative hypotheses

For primary safety hypothesis (complication-free rate), the following assumptions apply:

- Expected complication-free rate through 6 months: 95.0%
- H_A: Complication-free rate through 6 months post-implant > 90.0%

For primary efficacy hypothesis (LV pacing threshold for permanently programmed vector), the following assumptions apply:

- Expected rate of acceptable LV pacing thresholds at 3 months: 93.0%
- H_A: Acceptable LV pacing threshold rate at 3 months > 88.0%

Based on the above criteria, a total of 231 evaluable subjects assessed at 6 months would be required to accept the primary safety alternative hypothesis (endpoint 1). For primary endpoint 2, a total of 282 evaluable subjects assessed at 3 months would be required to accept the primary efficacy alternative hypothesis.

An adjustment of 10% is used in the sample size estimation for both primary endpoints 1 and 2 to account for subjects that exit the clinical investigation prior to having a 6 month evaluation. Reasons that subjects may exit the clinical investigation include withdrawal of consent, mortality, device explant, change in physician, or subject moving. Therefore, up to 314 subjects (=282/.9) will need to be enrolled to account for premature study terminations.

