2.5.4 Handling of Missing, Unused, or Spurious Data

All possible steps will be taken to minimize missing data in the clinical investigation. This includes but is not limited to monitoring of study forms for completeness and supporting efforts to track and maintain contact with study subjects during the study period. If any data is missing, the reason will be documented.

In cases of missing data, a pre-planned supplemental procedure using BIOTRONIK Home Monitoring® data to impute the missing data points will be followed. When active, BIOTRONIK Home Monitoring® provides daily automatic LV pacing thresholds, R-wave sensing, and pacing impedance. When available, missing data will be imputed with BIOTRONIK Home Monitoring® values obtained from the day of a completed follow-up, due date of a missed follow-up, or the next closest day before or after.

For values imputed in support of primary endpoint 2, the consistency of the imputed value will be examined by comparing the selected value to the average value of the surrounding 6 values (typically 3 values prior to the selected value and 3 values after the selected value). The imputed value will be considered consistent if it is contained within the 95% confidence interval for the surrounding 6 values or if the difference between the minimum and maximum of the imputed value and surrounding values is $\leq 0.2 V$.

Where BIOTRONIK Home Monitoring® data is not available for imputation of missing 3-month follow-up data in support of primary endpoint 2, the LV pacing threshold from the next completed follow-up after the 3-month time point may be used to impute the missing data.

Multiple analyses will be conducted as needed to assess the impact of missing and imputed data.

For purposes of the Kaplan-Meier survival analysis, described in Section 2.3.7, enrolled subjects exiting the clinical investigation prior to the 5 year visit will be censored at the time of study termination.

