3.5.2.5 Sentus QP lead extraction

Any subject who has the Sentus QP lead explanted and not replaced with another Sentus QP lead will be withdrawn from the clinical investigation. After documentation of the system revision procedure (see Section 3.4.7.2), a Study Termination eCRF should be completed.

Whenever possible, devices that are explanted must be returned to BIOTRONIK, Inc. for analysis.

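### Primary endpoint 2 counts a lead-caused implant failure as a failure, but a lead explanted for a lead-related event before 3 months and not replaced with another Sentus QP lead is imputed or dropped, which can only favour the acceptable-threshold rate

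*Combined protocol and SAP*

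**What the plan says.** Section 2.2.2 defines primary endpoint 2 as the percentage of subjects whose LV threshold at 3 months is at most 2.5 V at 0.4 ms in the permanently programmed vector. Section 2.3.3 tests this against 88.0% and lists two scenarios:

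- A subject not implanted because of a Sentus QP related adverse event is analysed as a failure.
- The second scenario begins "For successfully implanted subjects that missed a 3 month visit or did not undergo threshold testing of the LV lead". It also covers tests at another pulse width, and refers all of these subjects to Section 2.5.4.

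Section 2.5.4 imputes first from Home Monitoring, using the day of a completed visit, the "due date of a missed follow-up, or the next closest day before or after". If no such data exist, the next completed follow-up may be used. For endpoint 2, the Home Monitoring value is checked for consistency against six surrounding values.

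Section 3.5.2.5 states: "Any subject who has the Sentus QP lead explanted and not replaced with another Sentus QP lead will be withdrawn". Section 3.4.7.2 says the same, and adds that a subject who receives a new Sentus QP lead continues on the original schedule. Section 3.5.3 ends study procedures on the day of termination.

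On results, Section 1.4.2 reports: "A total of 286 subjects were included in the evaluation of primary endpoint 2". Of these, 267 were acceptable. Section 1.4.1 counts two subjects who "experienced an endpoint related adverse event but exited the study prior to reaching the 6 month follow-up".

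**The concern.** The two scenarios in Section 2.3.3 treat similar events differently. A lead that fails at implant because of a lead-related event is a failure. A lead that is implanted and then has to come out for a lead-related event before the 3-month test belongs to a successfully implanted subject, so the missing-data rule applies. If no new Sentus QP lead is placed, the subject has left the study. There is no later visit to borrow from, and any Home Monitoring threshold for that lead predates its removal. A lead removed for extracardiac stimulation, for instance, could contribute an acceptable threshold recorded before it was taken out. Without a usable value, the subject leaves the denominator.

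The missingness is caused by loss of the device under test, so it is informative. The handling also departs from the plan's own approach elsewhere: the endpoint 1 analysis (Section 2.3.2) keeps subjects with an early qualifying event. At stake is an upward bias in a co-primary effectiveness rate that was submitted in support of market approval.

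**Working it through.** **Inputs.** Section 2.4.1: "Test basis: exact binomial test", "Type I error, alpha: 2.5% (one-sided"), expected rate 93.0%, goal 88.0%, 282 evaluable, 314 enrolled. Section 1.4: cohort of 299. Section 1.4.2: 276 + 3 + 7 + 0 = 286 evaluable, 267 acceptable, 95% CI 89.8% to 96.0%, p = 0.002. Section 1.4.1: two subjects with an endpoint 1 event who exited before 6 months.

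**Plan's figures reproduced.** For n = 282, the smallest r with P(X ≥ r | n, 0.88) ≤ 0.025 is 259. The attained size is 0.0246 and the power at 0.93 is 0.812. This is the first n that reaches 80%, and 282/0.9 = 313.3, rounded up to 314. For the result, the exact lower bound is the 2.5% quantile of Beta(x, n − x + 1), and the one-sided p is P(X ≥ x | n, 0.88). With x = 267 and n = 286, the rate is 93.36%, the interval 89.82% to 95.95% and p = 0.0020. All agree with the documents.

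**Direction.** Take one lost lead, with x acceptable among the n other subjects. Failure scoring gives x/(n + 1).

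- Exclusion gives x/n, which is higher.
- An imputed value of at most 2.5 V gives (x + 1)/(n + 1), which is higher.
- An imputed value above 2.5 V gives x/(n + 1), which is equal.

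The planned handling is never below failure scoring.

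**How many subjects.** An explant for a lead-related event in the Table 7 categories is an endpoint 1 event, and without a new Sentus QP lead it ends participation. Such a subject would be among the two early exits in Section 1.4.1. That section does not say whether they left before or after a 3-month test, so the count is 0, 1 or 2.

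| Case | Acceptable/n | Rate | Exact lower bound | One-sided p |
|---|---|---|---|---|
| As reported (0 affected) | 267/286 | 93.4% | 89.8% | 0.002 |
| 1 had been dropped | 267/287 | 93.0% | 89.4% | 0.004 |
| 2 had been dropped | 267/288 | 92.7% | 89.1% | 0.006 |
| 2 had been imputed as acceptable | 265/286 | 92.7% | 89.0% | 0.007 |

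The largest shift is 93.36 − 92.66 = 0.70 points (0.65 if both had been dropped).

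**Distance to a changed conclusion.** Five added failures (267/291 = 91.8%, lower bound 87.98%) or five switched successes (262/286 = 91.6%, lower bound 87.8%) would be needed.

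**Effect on the design (assumed loss shares).** Suppose the true rate with losses counted as failures is exactly 88%, and a share l of subjects is lost and dropped. The rate among the 282 analysed is then 0.88/(1 − l). Applying r = 259, the type I error is 4.0% for l = 0.5%, 4.9% for l = 0.7% and 6.4% for l = 1%, against 2.5% with no loss. For scale, 2/288 = 0.7%.

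**The case against.** The case against has several parts.

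- **No text names explanted leads.** Section 2.3.3 presents its bullets as common scenarios, so the handling is inferred from several rules read together. This is true. But a successfully implanted subject without a 3-month test falls within the second bullet, and nothing takes an explanted lead out of it.
- **The Home Monitoring route may not operate.** A withdrawn subject arguably has no due date for a missed visit. The consistency check typically uses three later values, and an explanted lead may have none. Nothing shows that any of the three Home Monitoring imputations was such a case. This stands as a doubt about which route applies, but the alternative is exclusion, which also raises the rate.
- **Endpoint 1 already counts these losses.** Table 7 includes surgical explant for every listed event type, and whether a lead removed despite a good threshold is also a threshold failure is partly a choice of estimand. This stands in part. However, endpoint 2 is tested separately against its own goal, and the plan has already made that choice for failed implants.
- **Section 2.5.4 promises further analyses of missing and imputed data as needed.** It does, but it specifies none that scores these subjects as failures.
- **Endpoint 2 is finished.** The report went to FDA in November 2016 and this protocol version is dated February 2017. This stands, and it determines the form of the fix.

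A reader might extend the point to any explanted or abandoned lead. The documents do not support that. A subject given a new Sentus QP lead continues and can have a genuine 3-month threshold. No text withdraws a subject for an abandoned lead. The three subjects with no capture at testing were scored as failures.

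**Conclusion.** The point holds for one group: subjects whose lead was explanted for a lead-related event before the 3-month test and not replaced with another Sentus QP lead. For them the rules as written give a result that is never less favourable than failure scoring. In the pre-market data the effect is between 0 and about 0.7 points, and the lower bound stays at or above 89.0% against the 88.0% goal. The upper limit of two assumes that every such explant was counted as an endpoint 1 event, and that both subjects left before a 3-month test.

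Three stronger inferences are not supported:

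- **That the four evaluable categories in Section 1.4.2 confirm lost leads were dropped or imputed.** They contain no category for such leads, but they do not show that one occurred before 3 months.
- **That the result is fragile because five failures would reverse it.** Early exit with a lead event can supply at most two.
- **That the 299 − 286 = 13 subjects outside the analysis are lost leads.** The cohort includes implant attempts (Section 2.3.1), and no reasons for the 13 are given. Scoring all 13 as failures (267/299 = 89.3%, lower bound 85.2%) is an extreme with no basis in the documents.

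**What to change.** Add a scenario to Section 2.3.3. Successfully implanted subjects whose Sentus QP lead was explanted before the 3-month threshold test, because of an adverse event that the CEC adjudicated as related or possibly related to the lead, and who did not receive another Sentus QP lead, are scored as failures. Section 2.5.4 imputation is not applied to them. Subjects re-implanted with a Sentus QP lead keep their measured 3-month value.

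Since endpoint 2 has been analysed and submitted, apply the rule as a labelled sensitivity analysis alongside the submitted 267/286, not as a replacement for it. State how many of the two early exits it affects, and tabulate the reason for each of the 13 subjects outside the 286.

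The cost is a short text addition and a re-tabulation of data already held, with no new visits or measurements. The reported rate may fall by up to about 0.7 points, and the analysis is post hoc and must be described as such.
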